14.3 Clinical Safety Laboratory Test Data

14.3.1 Data Presentation

The PCS criteria used for the clinical safety laboratory are the Lundbeck standard PCS criteria described in SOP_09978: *GPV – PCS and standard reference values for laboratory investigations, vital signs and ECGs in clinical studies*, version 6, and are also included in [Table 2](#).

The clinical safety laboratory test values will be presented in both conventional and Système International (SI) units.

Fasting lipid and fasting glucose concentrations will be presented in separate tables from the overall laboratory tables.

For urine dipsticks, for which the results are categorical values (for example, negative, trace, 1+, 2+), the number and percentage of participants will be summarized by visit for each test.

The microscopy results will be listed by assessment time point for participants with findings.

14.3.2 Potential Drug-induced Liver Injury (DILI)

Signals of DILI will be assessed according to the FDA guideline² using the following criteria:

- ALT or AST $>2\times$, $>3\times$, $>5\times$, $>10\times$, or $>20\times$ ULN
- total bilirubin $>2\times$ ULN
- alkaline phosphatase $>1.5\times$ ULN
- ALT or AST $>3\times$ ULN AND total bilirubin $>1.5\times$ or $>2\times$ ULN

Participants fulfilling any of the criteria will be listed, and the listing will include all the ALT, AST, bilirubin, and alkaline phosphatase values for those participants, sorted by assessment date and time in ascending order. If a criterion for a test is fulfilled, the value will be flagged with the highest criterion fulfilled (for example, AST $>3\times$ ULN, $>5\times$ ULN, $>10\times$ ULN, or $>20\times$ ULN).

In addition, assessment time points for participants for whom Hy's Law is potentially fulfilled will also be flagged in the listing (pHYL):

- ALT or AST $>3 \times \text{ULN}$ AND
- alkaline phosphatase $<2 \times \text{ULN}$ AND
- total bilirubin $\geq 2 \times \text{ULN}$

The number of participants who met any of the criteria specified above at any post-baseline visit will be summarized. In the summaries, each participant will be counted only once using the maximum assessment, or the most severe for the combined criteria. The summaries will also include the number of potential Hy's Law cases.

14.4 Vital Signs and Weight

The PCS criteria used for vital signs and weight are the Lundbeck standard PCS criteria described in SOP_09978: *GPV – PCS and standard reference values for laboratory investigations, vital signs and ECGs in clinical studies*, version 6, and are also included in [Table 2](#).

Descriptive statistics for the vital signs, weight, and BMI, both absolute values and changes from Baseline, will be presented by visit. The number of participants exceeding the PCS values will be tabulated.

14.5 ECGs

The PCS criteria used for the ECG parameters are the Lundbeck standard PCS criteria described in SOP_09978: *GPV – PCS and standard reference values for laboratory investigations, vital signs and ECGs in clinical studies*, version 6, and are also included in [Table 3](#).

In addition to the tables and listings specified in section [14.2](#), absolute values and changes from Baseline in QTcF will also be summarized categorically by visit. The categories that will be used are as follows for the absolute QTcF values:

- QTcF interval < 450 msec
- QTcF interval 450 - 480 msec
- QTcF interval $> 480 - 500$ msec
- QTcF interval > 500 msec

The categories that will be used for the change from Baseline QTcF values are:

- QTcF interval increase from baseline > 30 msec
- QTcF interval increase from baseline > 60 msec

Furthermore, the number and percentage of participants being classified as having either a normal, abnormal but not clinically significant, abnormal and clinically significant, or not interpretable ECG result based on the overall interpretation of the ECG from the investigator will be summarized by visit.

14.6 Other Safety Endpoints

14.6.1 Columbia-Suicide Severity Rating Scale (C-SSRS) Scores

The C-SSRS was administered:

- for lifetime (using the *Baseline/Screening Version*) – the C-SSRS assessment at screening that collects a lifetime recall
- for the past 1 month at screening (using the *Baseline/Screening Version*) – the C-SSRS assessment at screening that focuses on the last month
- at Baseline (using the *Since Last Visit Version*) – the C-SSRS assessment at Baseline that collects information since the previous visit, for example, from screening to Baseline
- post-baseline (using the *Since Last Visit Version*) – the C-SSRS assessments after Baseline

The numbers and percentages of participants with lifetime, past 1 month, baseline, or post-baseline suicide-related events based on the C-SSRS will be summarized. For each summary, the most severe item with an answer “Yes” for each participant according to the ordering given in [Panel 4](#) is displayed. For the post-baseline assessments, the most severe score ([Panel 4](#)) per participants related to suicidal ideation and/or behaviour will be summarized.

The number and percentage of participants with *no suicidal ideation or behaviour* will be summarized.

Panel 4 C-SSRS Scores

C-SSRS Score	Related to:
1 Wish to be dead	Suicidal ideation
2 Non-specific active suicidal thoughts	
3 Active suicidal ideation with any methods (not plan) without intent to act	
4 Active suicidal ideation with some intent to act, without specific plan	
5 Active suicidal ideation with specific plan and intent	
6 Preparatory acts or behaviour	Suicidal behaviour
7 Aborted attempt	
8 Interrupted attempt	
9 Non-fatal suicide attempt	
10 Completed suicide (only applicable for the post-baseline assessments)	

The C-SSRS scores will be summarized based on the APTS for participants with at least one post-baseline C-SSRS assessment, regardless of whether they had a baseline C-SSRS assessment.

Missing C-SSRS scores will not be imputed.

Positive responses to *non-suicidal self-injurious behaviour* will be summarized separately.

For participants with any post-baseline suicidal ideation or behaviour (C-SSRS scores of 1 to 10), listings will be provided including all C-SSRS scores for those participants.

15 Immunogenicity

For participants with pre-existing antibodies at Baseline, the number and percent of participants who are positive for anti-epinezumab antibody will be summarized. In addition, for each scheduled visit and for the entire trial the number and percent of participants who are positive for anti-epinezumab will be summarized. Denominators for percentages will be the number of participants with a sample taken for the specified visit. For participants with ADA, neutralizing properties of anti-epinezumab antibodies will also be summarized. Participants with at least one visit with a positive ADA result (the confirmatory test being positive) will be considered as an ADA positive participant. Participants with no positive ADA results will be considered as ADA negative participants.

Participants' titer per visit and peak positive titer showing median, min, max and IQR for the peak values will be summarized.

Participants with first positive ADA result at the different visits and how many out of these had all the following results also being positive will be summarized. If missing values occur after a positive result this will also count as a following result being positive.

Participants with a positive anti-epinezumab antibody result will be listed. The listing will include visit, sampling assessment date, final ADA result, titre result and final Nab result.

In addition, summaries of TEAEs by SOC and preferred term will be provided for participants who are ADA-positive as well as ADA-negative. Furthermore, summaries of TEAEs of Hypersensitivity and Anaphylactic Reactions by SOC and preferred term will be provided for participants who are ADA-positive as well as ADA-negative.

Furthermore, adverse events in participants with positive anti-epinezumab antibody results or with pre-existing antibodies at Baseline will be provided. The listing will include the preferred term for the adverse event and start date and stop date of the adverse event.

16 Biomarker

The results from the analyses described in this section will be presented in an addendum to the clinical trial report.

The biomarker that will be presented is CGRP covered by the exploratory endpoint "Change from Baseline in CGRP (CGRP-epinezumab complex, free CGRP) (Week 0 after IMP infusion, and Weeks 12, 24, 36, and 48)" and will be considered for the values measured prior to an IMP infusion as well as the values after an IMP infusion.

The baseline values of CGRP-epinezumab complex and free CGRP will be summarized.

Numbers, arithmetic mean, standard deviation, median, lower and upper quartiles, minimum and maximum values as well as the percentage change from Baseline will be summarized by Visits before and after an IMP infusion for Weeks 12, 24 and 36 and once for Week 48.

The baseline value will be the value measured before the beginning of the first IMP infusion at the Baseline Visit.

For all other visits the acceptable ranges for measurements are defined as a value measured on the same date as an IMP infusion but prior to the IMP infusion being started is the measurement to be used as the prior value. A measurement made 55 minutes after the IMP infusion ended and the rest of that day will be assigned as the after IMP value.

17 Pharmacokinetic/Pharmacodynamic Analyses

A PK/PD analysis will be planned and conducted by PKPD modelling & simulation, H. Lundbeck A/S, and reported separately.

18 Data Reviews

The quality of the trial will be overseen by performing data reviews during the conduct of the trial. The reviews may include, but are not limited to, data quality, protocol adherence, and the appropriateness of design assumptions, including the sample size assumptions.

19 Interim Analyses

No interim analysis is planned.

20 Sample Size Considerations

In line with the ICH E1 guideline,³ the trial aims at providing data in 100 participants exposed to eptinezumab for 1 year. Dodick (2020),⁴ participants suffering from cCH included in a 12-week study, reports less than 4% withdrawals. In the European Union Drug Regulating Authorities Clinical Trials (EudraCT) report for study NCT02964338,⁵ in participants suffering from cCH, approximately 7% of participants dropped out from the first 12-week period; the withdrawals due to the “sponsor terminated study” are not included as a reason for withdrawal. As the withdrawal rate for a long-term study like the current trial is unknown, 125 participants are planned to be enrolled and treated, allowing for 100 participants to complete, with a withdrawal rate of 20%. The withdrawal rate will be monitored during the trial conduct, and if a clear deviation from the assumed withdrawal rate is observed, the number of participants enrolled and treated might be increased to ensure that data is available for a sufficient number of participants with long-term exposure.

21 Statistical Software

The statistical software used will be SAS®, Version 9.4 or later.

22 Changes to Analyses Specified in the Protocol

In the definition of FAS monthly has been changed to weekly to accommodate that there are endpoints considering weekly data.

There has been a clarification of the phrasing of the endpoints from the protocol. Furthermore, the names of the different types of endpoints have also been changed to describe these in a concise way.

The following endpoints have been added for completeness:

- Response: $\geq 75\%$ reduction from Baseline in the number of weekly attacks (Weeks 1-4, 13-16, 25-28, 37-40)
- Change from Baseline in the weekly integrated measure of frequency and intensity of pain, that is, the sum of the intensity (worst pain on a 5-point self-rating pain severity scale) for each attack during a week (Weeks 1, 2, 3, 4, 13, 14, 15, 16, 25, 26, 27, 28, 37, 38, 39, 40) or the intensity of pain multiplied by the weekly number of attacks (Weeks 5, 6, ..., 12, 17, 18, ..., 24, 29, 30, ..., 36, 41, 42, ..., 48)
- Use of triptans (Weeks 1-48)
- Use of oxygen (Weeks 1-48)
- Use of preventive medication (Weeks 1-48)
- Response: $\geq 75\%$ reduction from Baseline in the number of monthly attacks (Months 1,2, ..., 12)
- Sustained response: $\geq 75\%$ reduction from Baseline in the number of monthly attacks for any month, where all the subsequent Months also had $\geq 75\%$ reduction from Baseline in the number of monthly attacks (Month 1,2, ..., 12)
- A maximum score of mild in the 5-point self-rating pain severity scale (Months 1, 2, ..., 12)
- Change from Baseline in the number of weekly attacks (Weeks 1-4 and Weeks 1-2)
- Change from Baseline in the number of monthly attacks (Months 1-12)

The estimand part of the efficacy analyses were not included in the protocol. It has been added to the SAP for clarification.

The baseline score is log-transformed for MMRMs using number of weekly attacks, number of monthly attacks and weekly integrated measure of frequency and intensity of attack related pain.

23 Details on Data Handling

23.1 Data Structure

Information used for the efficacy analyses is either coming from the eDiary or from visits (both site visits and phone contacts). The structure of data depends on the source (eDiary or visit) and will be handled differently.

Because of the structure in the eDiary, all information is collected at a daily basis or at a weekly basis. This gives the possibility to look at data in three different ways:

1. Using the first 4 weeks after each IMP infusion providing 16 weekly scores (Weeks 1, 2, 3, 4, 13, 14, 15, 16, 25, 26, 27, 28, 37, 38, 39 and 40)
2. Using the 12 monthly scores for the entire trial (Months 1, 2, 3, 4, 5, 6, 7, 8, 9, 10, 11 and 12)
3. Using the 48 weekly scores for the entire trial (Weeks 1, 2, 3, 4, 5, 6, 7, 8, 9, 10, 11, 12, 13, ..., 45, 46, 47 and 48)

The rationale for considering these different ways of using data is:

1. The first four weeks after each IMP infusion are the periods with the most precise information (the participants complete the eDiary on a daily basis) and more likely it will be possible to use the most appropriate covariance structure
2. The months use as much information as possible since monthly scores are imputed across 4 weeks
3. All weeks show in more detail the development across time during the entire trial with a limitation in the choice of variance structure

Thus, if numbers (estimates) can be found from MMRMs using more than one of the above data structures the order of preference is if the data structure in 1) is applicable for finding the number of interest use this, if 1) is not appropriate and 2) is appropriate use 2), if neither 1) or 2) is appropriate then use 3). More specifically, for endpoints considering Weeks 1-4, 13-16, 25-28, 37-40 the results from 1) will be the most valid, for endpoints considering Months 1,2, ..., 12 the results from 2) will be the most valid, and for endpoints considering Weeks 1, 2, ..., 48 the results from 3) will be the most valid. The endpoints considering intervals across Weeks 1 to 48:

- Conversion from cCH to episodic cluster headache (eCH): no cluster headache attacks for ≥ 3 consecutive months (≥ 12 consecutive weeks) (Weeks 1-48)
- cCH remission: no cluster headache attacks for ≥ 1 month (≥ 4 consecutive weeks) (Weeks 1-48)
- cCH remission: no cluster headache attacks for ≥ 1 month (≥ 4 consecutive weeks) (Weeks 1-12, 13-24, 25-36, 37-48)
- Use of transitional treatment (Weeks 1-48)
- Use of triptans (Weeks 1-48)
- Use of oxygen (Weeks 1-48)
- Use of preventive medication (Weeks 1-48)

do not fit into either of the data structures in 1), 2) or 3) but will be assessed by a yes if the participant is fulfilling the criteria in the endpoint.

The ePRO data measured in connection with visits will be looked at in one way: the relevant week numbers corresponding to the visits will be considered in the analyses.

23.2 Derived Variables

23.2.1 eDiary

23.2.1.1 The 5-point Self-rated Pain Severity Scale Scores

The 5-point self-rated pain severity scale scores are used for several endpoints expressing the intensity of pain in different ways using distinct formulas. Common for them all is, that if the number of cluster headache attacks is reported to be 0, the corresponding pain will be set to be the category expressing no pain (no pain/barely any pain) since a participant will not be asked to rate the pain when 0 attacks are reported. The scores used in the analyses will be 0 (no pain/barely any pain) to 4 (excruciating pain).

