13.5.6 Efficacy Analysis

13.5.6.1 Continuous Efficacy Endpoints

In the eDiary, information regarding number of attacks, level of severity of pain of the attack(s) as well as use of abortive medication is gathered daily or weekly. When analysing data from the eDiary, three different data structures will be considered: weekly scores based on daily data, monthly scores based on weekly scores (regardless of the weekly scores originating from data being daily or weekly), and weekly scores based on either daily or weekly reported data covering all weeks which will be used descriptively to show the data over time (for further details see section [23.1](#)). The endpoints listed below are covered by applying the three different data structures in the MMRM as in section [13.5.1.2](#) using FAS and DPS3 with the relevant time variable, appropriate baseline value (for endpoints considering weekly/monthly attacks and integrated measure the log-transformed baseline

values will be used for all other endpoints there will be no transformation of the baseline values), and the appropriate contrast statement as well as a different list of covariance structures to get estimates of mean values, their standard errors (SEs) as well as two-sided 95% CIs:

- Change from Baseline in the weekly number of times an abortive therapy (oxygen and/or triptans) was used (Weeks 1-4, 13-16, 25-28, 37-40)
- Change from Baseline in the number of weekly attacks (Weeks 1-4, 13-16, 25-28, 37-40)
- Change from Baseline in the average attack related daily pain (including days with no attacks), as assessed using the 5-point self-rating pain severity scale (Weeks 1, 2, 3, 4, 13, 14, 15, 16, 25, 26, 27, 28, 37, 38, 39, 40)
- Change from Baseline in the number of monthly attacks (Months 1,2, ..., 12)
- Change from Baseline in the pain per attack assessed by the 5-point self-rating pain severity scale scores (Months 1,2, ..., 12)
- Change from Baseline in the monthly number of times an abortive therapy (oxygen and/or triptans) was used (Months 1,2, ..., 12)

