23.2.1.3 Imputation of Missing Post-baseline eDiary Assessments

The strategy of imputation of missing values is given by:

1. For each weekly score in the periods with daily entries in the eDiary, prorating is used to impute any missing data when data have been observed for at least 4 days in a week, to have full weekly scores
2. For each monthly score, prorating is used to impute any missing data when data have been observed for at least 2 weeks in a month (after prorating weekly scores), to have full monthly scores

For a 7-day weekly period where the eDiary is completed in at least 4 out of 7 days, the number of attacks will be calculated using prorating:

$7 * (\text{Reported number of daily attacks/Reported eDiary Days})$

For participants where the eDiary is completed in 3 days or less, the 7-day weekly observation will be set to missing.

For a 4-week monthly period where the eDiary is completed in at least 2 out of 4 weeks, the number of attacks will be calculated using prorating:

$4 * (\text{Number of weekly attacks/Reported eDiary Weeks})$

For participants where the eDiary is completed in 1 week or less the 4-week monthly observation will be set to missing.

Use of abortive medication is prorated using the same criteria and formulas as above where *Reported number of daily attacks* is replaced by *Reported number of daily times an abortive medication was taken* and *Number of weekly attacks* is replaced by *Number of weekly times an abortive medication was taken*.

The severity of attacks is prorated using the same criteria as above using the same formulas as in section [23.2.1.2](#).

The derivation of the three pain scores can be seen in [Panel 5](#). When calculating the average attack related daily pain and the weekly integrated measure of frequency and intensity of attack related pain, a value of 0 will be added to the nominator and count as a day in the denominator for days/weeks with 0 attacks. Furthermore, the weekly pain per attack is not defined for days/weeks with 0 attacks.

Panel 5 Definitions of Post-Baseline Pain Scores

	Daily eDiary	Weekly eDiary
Average attack related daily pain	Sum of the average daily pain across days with data/number of days with data	NA
Weekly pain per attack	Sum of pain across attacks/number of attacks	Pain
Monthly pain per attack	Sum of the weekly pain per attack scores/ number of the weekly pain per attack scores	

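### SAP 23.2.1.1 scores every attack-free week as pain 0, while 23.2.1.3 leaves pain per attack undefined in such weeks; the two rules give different monthly values from the same diary

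*SAP*

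**What the plan says.** SAP 23.2.1.1 introduces the pain-scale scores. It notes that they use different formulas and then states a shared rule: "Common for them all is, that if the number of cluster headache attacks is reported to be 0", the score is taken as the lowest category, that is 0. The reason given is that a participant who reports no attacks is not asked to rate pain. Scores run from 0 to 4.

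SAP 23.2.1.3 gives the post-baseline derivations. It adds a zero for two named scores: "When calculating the average attack related daily pain and the weekly integrated measure of frequency and intensity of attack related pain, a value of 0" goes into the numerator for attack-free days or weeks. Pain per attack is not among them, and the section adds that "the weekly pain per attack is not defined for days/weeks with 0 attacks".

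Panel 5 in the same section defines weekly pain per attack as total pain divided by number of attacks in daily-diary weeks, and as the reported pain rating itself in weekly-diary weeks. Monthly pain per attack is "Sum of the weekly pain per attack scores/ number of the weekly pain per attack scores".

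The minimum for a monthly score is worded in two ways in 23.2.1.3: data observed in at least 2 weeks, and the eDiary completed in at least 2 of 4 weeks. Below that, "For participants where the eDiary is completed in 1 week or less the 4-week monthly observation will be set to missing". The same criteria are extended to attack severity.

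The endpoint is "Change from Baseline in the pain per attack assessed by the 5-point self-rating pain severity scale scores", Months 1 to 12 (SAP 13.5.6.1). Panel 2 lists it as exploratory, and SAP 13.2 plans no formal testing.

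**The concern.** Read literally, the shared rule in 23.2.1.1 covers pain per attack, and 23.2.1.3 says that this score does not exist in the same weeks. The difference is one of meaning. With attack-free weeks scored 0, the monthly value falls as attacks become rarer, even if each remaining attack hurts as much as before, so it becomes a second measure of frequency. With those weeks undefined, it describes the severity of the attacks that still occur. The baseline value (SAP 23.2.1.2) is total pain divided by number of attacks, which attack-free days cannot change. The zero rule would therefore compare unlike quantities.

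The months affected are those of participants who improve most. SAP Panel 2 itself plans for such months, with endpoints for remission (at least 4 consecutive attack-free weeks) and for a 100% monthly reduction.

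**Working it through.** The plan states no figure on this point, so there is none to reproduce. The check applies the Panel 5 monthly formula to one diary under each reading.

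**Inputs**
- Scale 0 to 4 (SAP 23.2.1.1).
- Monthly score = mean of the weekly pain-per-attack scores (SAP 23.2.1.3, Panel 5).
- All four weeks of the month completed; pain in attack weeks equal to baseline, so the attacks themselves have not changed.
- Baseline pain per attack of 3 (severe). This is an assumption, as the documents give no value; 2 and 4 are shown as the range.

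**Readings**
- A: attack-free week = 0 (23.2.1.1).
- B: attack-free week undefined (23.2.1.3), and the 2-week minimum counts completed diary weeks.
- C: attack-free week undefined, and the 2-week minimum counts weeks with a defined score.

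**One attack week, three attack-free weeks, baseline 3**
- A: (3 + 0 + 0 + 0)/4 = 0.75; change 0.75 - 3 = -2.25.
- B: 3/1 = 3; change 0.
- C: one defined score, below 2, so missing.

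The gap between A and B is 2.25/4 = 56% of the scale.

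**Change from a baseline of 3, by number of attack weeks**

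| Attack weeks | A | B | C |
|---|---|---|---|
| 0 | -3 | no value | no value |
| 1 | -2.25 | 0 | missing |
| 2 | -1.5 | 0 | 0 |
| 3 | -0.75 | 0 | 0 |
| 4 | 0 | 0 | 0 |

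**Range, one attack week**
- Baseline 2: A = 2/4 - 2 = -1.5; B = 0.
- Baseline 4: A = 4/4 - 4 = -3.0; B = 0.

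**Where the conflict bites.** Weekly diaries cover 8 weeks after each of four infusions from the fifth week on: 4 x 8 = 32 of 48 weeks, or Months 2, 3, 5, 6, 8, 9, 11 and 12. There Panel 5 takes the pain rating directly, and in an attack-free week the only rating available is the 0 that 23.2.1.1 assigns. In daily-diary weeks (Months 1, 4, 7 and 10) the formula is 0/0 when there are no attacks, so it is undefined anyway. A program that coded raw pain as 0 and then followed the two Panel 5 cells literally could give the one-attack-week participant 0 in Month 1 and -2.25 in Month 2, from the same attack pattern.

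**Attack-free months.** Under B or C these have no value. The MMRM is fitted to the remaining months, and its likelihood treats the absent ones as missing at random, although they are absent because the participant had no attacks. The sensitivity analyses in SAP 13.5.9 cover the two estimand endpoints and 75% response, not this one.

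**The case against.** The best defence is that 23.2.1.3 is the derivation section and the more specific rule. It names the scores that receive a zero, leaves pain per attack out, and says that this score is undefined in attack-free weeks as well as days. Panel 5 divides by the number of weekly scores, so undefined weeks drop out of the denominator. Section 23.2.1.1 can be read as merely coding a question that was not asked. This stands as the likelier reading, and on it the worked month gives 0. It does not remove the conflict: the shared rule in 23.2.1.1 has no exception, and the weekly-diary cell of Panel 5 will accept the zero.

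A reader might also infer that the one-attack-week month is simply set to missing. The documents do not support that. The rule quoted for missing months concerns completion of the eDiary, and a week reported with 0 attacks is a completed week. The month is missing only if the minimum is taken to count defined scores, which 23.2.1.3 does not say, although it does not say how an undefined week counts either.

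The stakes are limited. This is one exploratory endpoint in an open-label, single-arm trial without formal testing. Average attack-related daily pain, the integrated measure and the maximum-pain endpoint already score attack-free time explicitly, and both sections agree on them. The planned 100% response endpoint already reports how many observed participants were attack-free each month.

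**Conclusion.** The contradiction is real and should be removed. For a completed month with one attack week, the change in pain per attack is -2.25 under 23.2.1.1 and 0 under 23.2.1.3 with a baseline of 3, and -1.5 or -3.0 against 0 with a baseline of 2 or 4. An attack-free month gives -3 or no value at baseline 3. These are worked figures for a single participant on an assumed baseline. The effect on a group mean depends on how many attack-free weeks occur, and the documents do not give that.

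Two stronger conclusions are tempting and do not follow. The readings are not equally open, since 23.2.1.3 is the more specific. Nor do the undefined months show that the MMRM must be dropped: for an exploratory, untested endpoint that is a matter of judgement, and a table restricted to participants with attacks carries the same selection. What is needed is a stated rule and a clear account of which months the estimate describes.

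**What to change.** 1. In SAP 23.2.1.1, exempt pain per attack from the zero rule. Keep the rule for average attack-related daily pain, the integrated measure and the maximum-pain endpoint.
2. In SAP 23.2.1.3, state that for monthly pain per attack the 2-of-4-week minimum counts completed diary weeks, including those with 0 attacks, and that the score is the mean over weeks with attacks. Do not relax this to a single observed attack week: that would admit months with three unreported weeks, which the section now excludes.
3. Keep the MMRM. Beside it, by month, give descriptive statistics among participants with at least one attack, the number contributing and the number attack-free, and say that the estimate concerns months with attacks.

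The cost is a few sentences of SAP text and one extra descriptive table for an exploratory endpoint. No data collection changes.
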